### PROTOCOL REVISION HISTORY

Edits were made throughout the protocol. Substantive changes are listed below.

### Protocol Version 2.0

- 1. Section 2.3.2.1 Change in Total Neuropathy Score modality.
- 2. Section 4.2.6: Clarification of exclusion criteria regarding prior participation in non-pharmacologic activities or classes such as mindfulness classes and scrambler therapies.
- 3. Section 6.1.1: Addition of Deep 6 Language regarding pre-screening.
- 4. Section 7.2.2: Addition of updated version of the Common Terminology Criteria for Adverse Events (CTCAE v.5)
- 5. Appendix: Addition of concomitant medications of interested (analgesics)
- 6. Appendix: Addition of Total Neuropathy Score Clinical Sheet

### Protocol Version 3.0

- 1. Section 4.1, Inclusion Criteria: Removed the requirement for patients to speak English to allow for enrollment of non-English speakers.
- 2. Sections 6.1.2.1.1, 6.1.2.1.2 & 6.1.2.2: Removed online consent checklist, updated phone consent plan to align with current CCTO practices
- 3. Section 6.2.2, Procedures During Treatment & Schedule of Events Table: Added  $\pm$  2 days window for the reminder calls at Day 3, Day 7, Day 31 and Day 35

### Protocol Version 4.0

1. Removal of Exclusion Criteria 4.2.2: Medical history of neuropathy from any type of nerve compression (e.g., carpal tunnel or tarsal tunnel syndrome, radiculopathy, spinal stenosis, brachial plexopathy, leptomeningeal carcinomatosis), as assessed by treating physician.

### Protocol Version 5.0

- 1. 7.4 Safety Reporting Requirements updated to reflect most current process
- 2. Replacement of Docusign to RedCap for e-consenting method
- 3. 9.7 Adherence to Protocol updated to reflect most current process

### Protocol Version 6.0

1. Additional of the Torrance Site at the Hunt Cancer Center, local staff added to the protocol.

### **LIST OF ABBREVIATIONS**

AE Adverse Event

CIPN Chemotherapy-Induced Peripheral Neuropathy
CTCAE Common Terminology Criteria for Adverse Events

ESAS Edmonton Symptom Assessment System

FACT/GOG-NTX Functional Assessment of Cancer Therapy/Gynecologic Oncology Group —

Neurotoxicity

FDA Food and Drug Administration
HPT High Performance Technology
IRB Institutional Review Board

TNSc Total Neuropathy Score clinical

NCI National Cancer Institute

PROMIS Patient-Reported Outcomes Measurement Information System

[figure not shown]
SOCCI Samuel Oschin Comprehensive Cancer Institute

TSH Thyroid-Stimulating Hormone

TUG Timed Up and Go

UPIRSO Unanticipated Problem Involving Risks to Subject or Others

## STUDY SCHEMA

### STUDY SUMMARY

Title	Voxx Human Performance Technology Socks for Chemotherapy- Induced Peripheral Neuropathy: A Double Blind, Randomized, Controlled Crossover Trial
Protocol Number	IIT2019-08-[name]-VOXXSOCK
Phase	Pilot
Methodology	Double blind, randomized, crossover
Study Duration	1 year
Study Center(s)	Cedars-Sinai Medical Center
Objectives	
 
Primary Objective: To gather preliminary data on the impact of Voxx HPT Socks compared to placebo socks on chemotherapy-induced peripheral neuropathy in patients with cancer.
 
Secondary Objectives:         
 
To assess the impact of Voxx HPT Socks compared to placebo socks on quality of life in patients with cancer experiencing chemotherapy-induced peripheral neuropathy.
 
To assess the impact of Voxx HPT Socks compared to placebo socks on the experience of cancer-related symptoms in patients with cancer experiencing chemotherapy-induced peripheral neuropathy.
 
To assess the feasibility of using Voxx HPT Socks to treat chemotherapy-induced peripheral neuropathy in patients with cancer.
 
 
 

Number of Subjects	We will enroll up to 30 participants in order to have 20 evaluable participants total.
Diagnosis and Main Inclusion Criteria	
 
Stage 1-4 cancer (all types)
 
Completed taxane- or platinum-based chemotherapy, vinca alkaloids, or bortezomib at least three months (90 days) ago. Current use of anti-estrogen therapy, Herceptin, or PARP inhibitors is okay.
 
Self-reported average neuropathic pain score of at least 4 on a 10-point scale over the past 1 month.
 
Clinician's diagnosis of chemotherapy-induced peripheral neuropathy
 
Must not have participated in a non-pharmacologic therapy specifically for the treatment of chemotherapy-induced peripheral neuropathy, including Scrambler Therapy, mindfulness meditation, or other mind-body activities within 14 days (2 weeks) prior to randomization.
 
Concomitant use of analgesics is permitted if the dose has been stable for at least 2 weeks prior to study enrollment
 
Age ≥ 18 years.
 
Written informed consent obtained from subject and ability for subject to comply with the requirements of the study.
 

### 1.0 BACKGROUND AND RATIONALE

### 1.1 Background

Chemotherapy-induced peripheral neuropathy (CIPN) symptoms are a common sequelae of neurotoxic chemotherapies (e.g., taxanes, platinums, vinca alkaloids, bortezomib) and have been reported in 20-60% of patients following treatment. CIPN symptoms include pain, numbness, tingling, impaired sensory function, and neuropathic pain in the hands and feet. CIPN symptoms are at times severe enough to require reductions in chemotherapy dose, which may impair treatment efficacy. Although reversible if treated early, CIPN often becomes chronic, persisting for years following chemotherapy and causing significant decrements to functioning and quality of life. To date, few effective treatments have been identified. Although ASCO recommends duloxetine, it is felt to have only a modest benefit and is associated with several unpleasant side effects. Sensory impairments predominate in chronic CIPN, and treatments for these problems have not been developed.

### 1.2 Rationale

Voxx human performance technology (HPT) is reported to use proprietary technology to improve energy, strength, and balance. Via a specific pattern, Voxx HPT is reported to stimulate cutaneous sensory mechanoreceptors on the bottom of the feet. In turn, a precise afferent neural response activates the brainstem regulatory function via the peripheral nervous system. The Voxx HPT proprietary pattern is woven into a sock and is drug and electrical free. Anecdotal reports have suggested benefit for a variety of conditions including chronic pain, enhanced postural stability and balance, and improved energy. No formal clinical trials have been published to date in PubMed although a recent study (unpublished) found a clinically and significant decrease among patients with painful diabetic neuropathy using HPT after 1 week of use.

The objective of this double blind, randomized, crossover pilot study is to gain preliminary data on the effects of Voxx HPT Socks versus placebo socks for the treatment of chemotherapy-induced peripheral neuropathy in patients with cancer who have completed platinum and taxane-based chemotherapies.

This research is highly relevant to cancer as CIPN is one of the most challenging side effects of cancer treatment and can substantially impair critical daily activities such as driving and exercise and impair fine motor activities involving the use of hands, thus significantly impairing quality of life. CIPN can also result in early discontinuation of treatment, thus interfering with treatment dose and efficacy.

### 2.0 STUDY OBJECTIVES

### 2.1 Primary Objective

2.1.1 To gather preliminary data on the impact of Voxx HPT Socks compared to placebo socks on chemotherapy-induced peripheral neuropathy in patients with cancer.

### 2.2 Secondary Objectives

- 2.2.1 To assess the impact of Voxx HPT Socks compared to placebo socks on quality of life in patients with cancer experiencing chemotherapy-induced peripheral neuropathy.
- 2.2.2 To assess the impact of Voxx HPT Socks compared to placebo socks on the experience of cancer-related symptoms in patients with cancer experiencing chemotherapy-induced peripheral neuropathy.

2.2.3 To assess the feasibility of using Voxx HPT Socks to treat chemotherapy-induced peripheral neuropathy in patients with cancer.

### 2.3 Endpoints

### 2.3.1 Primary Endpoint

2.3.1.1 Impact on chemotherapy-induced peripheral neuropathy will be subjectively measured by changes in scores on the Functional Assessment of Cancer Therapy/Gynecologic Oncology Group – Neurotoxicity (FACT/GOG-NTX) Neurotoxicity Subscale.

### 2.3.2 Secondary Endpoints

- 2.3.2.1 Impact on chemotherapy-induced peripheral neuropathy will be objectively measured by changes in scores on the Total Neuropathy Scale clinical I(TNSc) and Timed Up and Go (TUG) test.
- 2.3.2.2 Impact on quality of life will be measured by the changes in scores on the Patient-Reported Outcomes Measurement Information System 29 (PROMIS-29).
- 2.3.2.3 Impact on cancer-related symptom experience will be measured by changes in scores on the Edmonton Symptom Assessment Scale (ESAS).
- 2.3.2.4 Feasibility will be measured by the number of hours the socks are worn, as recorded in the patient's daily sock diary.

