### Sock Dispensing

Patients on Arm A will be given 6 pairs of Voxx HPT socks along with a start date on when the patient should begin wearing the socks (start date = Day 1). Patients will be asked to wear the socks continuously during both waking and sleeping hours for two weeks from that start date, except when showering, bathing, or swimming.

Patients on Arm B will be given 6 pairs of placebo socks along with a start date on when the patient should begin wearing the socks (start date = Day 1). Patients will be asked to wear the socks continuously during both waking and sleeping hours for two weeks from that start date, except when showering, bathing, or swimming.

Patients will be told that the socks can be washed on delicate cycle and worn repeatedly. Patients will be asked not to let others wear the socks during the course of the trial.

The investigator and patient will be blinded to treatment assignment.

Daily Sock Diary Instruction

Patients will be given the Daily Sock Diary form and asked to keep a daily record of approximately how many hours the socks were worn, and whether the socks were worn while sleeping.

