### **WEEK 3 (WASHOUT)**

• T1 – Day 15 (+3 days)

All procedures below are completed for research only.

Concomitant Medications of Interest

Current medications of interest will be abstracted through medical record review at T1 visit.

- TNSc Physician or Nurse Assessed
- o TUG
- Questionnaires (can be emailed, mailed, or given in person)
  - FACT/GOG-NTX v4, Neurotoxicity Subscale
  - PROMIS-29
  - ESAS
- Sock Diary Submission Patients will be asked to submit their daily sock diaries to the coordinator.
- Sock Return Patients will be asked to return all study socks to the study coordinator.
- Sock Dispensing Patients will be given 6 new pairs of socks, according to assigned arm:
  - Patients on Arm A will be given 6 pairs of placebo socks along with a start date on when the patient should begin wearing the socks (start date = Day 29). Patients will be asked to wear the socks continuously during both waking and sleeping hours for two weeks from that start date, except when showering, bathing, or swimming.
  - Patients on Arm B will be given 6 pairs of Voxx HPT socks along with a start date on when the patient should begin wearing the socks (start date = Day 29). Patients will be asked to wear the socks continuously during both waking and sleeping hours for

- two weeks from that start date, except when showering, bathing, or swimming.
- Patients will be reminded that the socks can be washed on delicate cycle and worn repeatedly. Patients will be reminded not to let others wear the socks during the course of the trial.
- The investigator and patient will be blinded to treatment assignment.
- Daily Sock Diary Instruction Patients will be reminded to keep a
  daily record of approximately how many hours the socks were worn
  and to note whether the socks were worn while sleeping.

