### **WEEK 4** (WASHOUT)

• Day 28 – One Day before Crossover Treatment Start Date (-2 days)
A phone call will be made to the patient to remind them to start wearing their socks the following day (Day 29), and to keep daily records of approximately how many hours the socks were worn.

### WEEK 5

- Continuous Sock Wearing
- Daily Sock Diary Entries
- Reminder Calls

Phone calls will be made to the patients on Day 31(+/- 2 Days) and Day 35(+/-2 Days) to remind the patients to wear their socks and to monitor for any adverse events. Thereafter, patients will be able to call a study coordinator with any questions or concerns.

### WEEK 6

- Continuous Sock Wearing
- Daily Sock Diary Entries

Any patient who stops study treatment early will be encouraged to return to the study center for all study visits. The reason(s) for any study or assessment discontinuation will be documented.

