### **8.0 STATISTICAL CONSIDERATIONS**

**Sample size and randomization:** This is a pilot crossover study to collect data on effect sizes for the outcomes. Patients will be randomized to one of two treatment sequences as Voxx socks then placebo socks, or placebo socks then Voxx socks. We will enroll 30 patients to allow for dropout to obtain 20 evaluable patients.

**Statistical Methods:** The fundamental analytic approach will be based on a within-subjects comparison of the main outcome measured with Voxx socks versus that measured on placebo in this crossover trial. The primary approach will used linear mixed models with time and treatment effects, adjusted for the repeated measures of subjects nested within sequence in the correlation structure. Carry-over effects will be tested by examining the interaction between treatment and period. In the unlikely event of a statistically significant carry over effect, only data from the first period will be used for the analysis. The overall type I error rate for the primary outcome measure will be controlled at 5%. The main outcome is the score on the Functional Assessment of Cancer Therapy/Gynecologic Oncology Group — Neurotoxicity (FACT/GOG-NTX) Neurotoxicity Subscale.

Data will first be assessed for reliability and general integrity (e.g., distribution characteristics) to ensure that appropriate statistical techniques are applied. Our basic approach to the analysis assumes there are no carry-over effects between the two treatment periods. All subjects entered into the trial will be included in the analysis. Strictly speaking, this is not an "intent-to-treat" policy because the crossover design should assure that each participant receives both Voxx socks as well as placebo in the appropriate treatment periods. If a study participant did not receive one or both treatments, they cannot be included in the primary analysis because that analysis relies on within-subject differences between the treatments. The status of all participants will be reported in the analysis as in the CONSORT recommendations. The fundamental analytic approach will be based on a within-subjects comparison of the relevant outcome measured on Voxx socks versus that measured on placebo. Secondary endpoints will be analyzed the same way as the primary endpoint.

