For all secondary objectives, a significance level of 0.05 will be used. A patient will be considered to have completed treatment if they have completed FACT/GOG-NTX at baseline, both treatment periods, and at least 50% compliance for both treatment periods. Compliance will be defined as wearing the socks for at least 16 hours per day.

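### The both-treatments restriction in Section 8, carried over to feasibility, removes patients who give up in period 1, so the wear estimate would describe those who persisted

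*Combined protocol and SAP*

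**What the plan says.** Objective 2.2.3 is to assess the feasibility of using the Voxx socks. Its only endpoint is in 2.3.2.4: "Feasibility will be measured by the number of hours the socks are worn", with the hours taken from the diary that each patient keeps. No summary statistic, denominator or success threshold is given. Under Sock Dispensing, patients are "asked to keep a daily record of approximately how many hours the socks were worn, and whether the socks were worn while sleeping". Diaries are collected at T1 (Day 15) and T2 (Day 43): "Patients will be asked to submit their daily sock diaries to the coordinator".

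Three statements in Section 8 bear on who is counted:

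- One sentence includes every subject who entered the trial.
- A more specific sentence soon after reads: "If a study participant did not receive one or both treatments, they cannot be included in the primary analysis". The reason given is that the primary analysis depends on differences within a subject.
- The paragraph closes: "Secondary endpoints will be analyzed the same way as the primary endpoint".

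Section 8 also promises a CONSORT-style account of all participants. Section 6.2.2 adds: "Any patient who stops study treatment early will be encouraged to return to the study center for all study visits". The reasons for discontinuation are to be documented.

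**The concern.** A feasibility endpoint asks whether patients who are given the socks manage to wear them nearly round the clock. Those who give up carry most of the information. A restriction designed for a within-patient efficacy contrast is extended here, by one general sentence, to an endpoint where it removes those patients.

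The reason for the restriction does not carry over. Hours of wear in one period can be summarised without a second period. For an Arm A patient who stops in period 1, the discarded hours are hours on the Voxx socks themselves, which is what objective 2.2.3 is about.

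At stake is the reading of that objective: a mean taken over persisters could be presented as the wear to expect from patients offered the socks.

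**Working it through.** **Tracing the rule.** Take an Arm A patient who stops on Day 4 and is never given the second set of socks.

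1. The patient received one treatment, so the Section 8 restriction bars them from the primary analysis.
2. Feasibility is listed as 2.3.2.4, under secondary endpoints.
3. Section 8 analyses secondary endpoints as it does the primary, so the restriction applies to feasibility.
4. Returning the diary does not help, because the exclusion depends on treatment received and not on diary data.
5. The sentence that includes all entered subjects would keep this patient. The two sentences cannot both hold, and the specific one is the one with a stated reason.

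Section 8 does not say whether a treatment counts as received when the socks are dispensed or when they are worn. A patient who takes the second set and leaves it unworn could fall either side.

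**Plan's own figures.** No feasibility figure is stated, so there is none to reproduce. Section 8 enrols 30 to obtain 20 evaluable, an implied loss of 1 − 20/30 = 33.3%. Working back, 20/(1 − 1/3) = 30, which agrees but is circular.

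**Size, by illustration for period 1.** Inputs:

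- n = 30 patients (Section 8).
- m = patients missing from the estimate: 3, 6 or 10, where 10 is the whole planned gap.
- h = mean among analysed patients, assumed 20 h/day.
- w = mean among missing patients, assumed 0, 10 or 20 h/day. A patient who wears the socks 20 h/day for 7 days and then stops has w = (20 × 7)/14 = 10.

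The reported mean is h. The all-patient mean is [h(n − m) + w·m]/n.

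| m | w = 0 | w = 10 | w = 20 |
|---|---|---|---|
| 3 | 540/30 = 18.0 | 570/30 = 19.0 | 20 |
| 6 | 480/30 = 16.0 | 540/30 = 18.0 | 20 |
| 10 | 400/30 = 13.3 | 500/30 = 16.7 | 20 |

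With m = 10 and w = 0, other values of h give 10.7 (h = 16), 12.0 (h = 18) and 14.7 (h = 22).

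**Blank days, a separate matter.** For one patient recording 20 h/day with b of 14 days blank, the recorded-days mean is 20 and the zero-filled mean is 20(14 − b)/14. That is 18.6 for b = 1, 15.7 for b = 3 and 10.0 for b = 7. If the socks were worn on the blank days, 20 is correct and zero-filling understates wear.

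**The case against.** The best defence is that Section 8 includes all entered subjects, early stoppers are encouraged to attend the visits at which diaries are collected, and the fate of every participant is reported. Dropout would therefore be visible. That is true, but it does not restore the lost hours: the specific exclusion still applies, attendance does not override it, and a participant flow account is not a wear estimate. It is also fair that this is one secondary endpoint in a pilot, with no feasibility threshold and so no planned decision resting on it. That limits the consequence.

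Several stronger readings are tempting, and the documents do not support them:

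- *Blank days and unreturned diaries fall out of the endpoint.* The plan is silent on both. If the endpoint is a total of hours, a blank day adds nothing and already counts as non-wear. Only a mean over recorded days would drop it, and the plan does not specify one.
- *Feasibility is overstated by a known amount.* Overstatement is the likely direction for excluded early stoppers, but its size rests on assumed hours. Treating all 10 patients between 30 and 20 as missing is an upper limit. Evaluable is not defined, and a patient could be non-evaluable for a missing questionnaire while returning a full diary.
- *The compliance rule distorts feasibility.* The requirement of "at least 50% compliance for both treatment periods", with compliance set at 16 hours per day, defines treatment completion and is not linked to 2.3.2.4. Its denominator is unstated, but a patient with 7 compliant days and 7 blank days reaches 7/14 = 50% even on all 14 days, so status does not change.
- *Every blank should be scored as zero.* That can bias the estimate the other way.

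**Conclusion.** The point holds for patients who do not receive both treatments. This is the effect of a stated rule, not only of a gap: followed literally, Section 8 excludes from feasibility those who quit in period 1 and never start period 2, in conflict with its own all-subjects sentence. The resulting figure describes persisters and would probably overstate feasibility, on the assumption that those who quit wore the socks less than those who continued.

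The size is unknown. Under the illustration, a reported 20 h/day is compatible with an all-patient mean from 13.3 h/day (10 of 30 missing, no wear) to 20 h/day (missing patients wore the socks equally). The low end is below the 16 h/day used in the completion definition, though that figure is a yardstick here and not a feasibility criterion. For blank days and unreturned diaries, the finding is only that the handling is unspecified. The plan should be changed, but the primary endpoint is not affected.

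**What to change.** In 2.3.2.4 and Section 8:

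- State that feasibility is exempt from the both-treatments restriction, and reconcile that restriction with the all-subjects sentence.
- Summarise wear over all patients dispensed socks, by sock type and period, with a 14-day denominator for each period in which socks were dispensed.
- Count days after documented stopping as 0 hours. The plan requires the reason for stopping to be recorded but mentions no date, so record the date too.
- Show blank days and unreturned diaries as a range, with recorded days only as the upper bound and zero-filled as the lower bound.
- Report diary return, the number of unrecorded days, and the number who never started period 2. The last is needed because the period 2 summary still covers only those who reached it.

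The cost is revised wording in two places, a stop date on the form, one extra summary, and a feasibility figure that may look less favourable. The primary analysis is untouched.

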### 3.0 STUDY DESIGN

This is a double blind, randomized, crossover pilot study of Voxx HPT Socks versus placebo socks for the treatment of chemotherapy-induced peripheral neuropathy in patients with cancer. We will enroll up to 30 patients in order to have 20 evaluable patients total. Patients will be randomized 1:1 to one of the following regimens:

- Arm A: Continuous wear of Voxx HPT Socks for 2 weeks, followed by continuous wear of placebo socks for 2 weeks (separated by a 2-week washout period)
- Arm B: Continuous wear of placebo socks for 2 weeks, followed by continuous wear of Voxx HPT Socks for 2 weeks (separated by a 2-week washout period)

Patients will be evaluated at three timepoints using an objective neuropathy assessment as well as self-report questionnaires assessing chemotherapy-induced peripheral neuropathy, quality of life, and cancer-related symptoms (see Section 6.3 for assessment timepoints).

